2.2.1 Secondary Objectives

1. To compare the proportion of patients with virological suppression at 24 months in patients receiving care via community ART models with those receiving care in the clinic (standard of care).

2. To compare Loss to Follow-up (LTFU) rates and missed dispensation of ARVs among individuals receiving care via community ART models with those receiving care in the clinic (standard of care), measured using routine health centre data

3. To compare HIV disease progression, and death among individuals receiving care via community ART models with those receiving care in the clinic (standard of care), measured using:

- CD4 cell count, WHO staging events, death from routine health centre data.

4. To qualitatively assess how health staff (including CHiPs) and PLWH on treatment experience the two models of care. This would be achieved through:

- Documenting treatment, adherence and retention experiences of PLWH accessing treatment through adherence club and home delivery models;

- Exploring the impact of the two models of care on access to treatment, adherence and retention according to the experience and perspectives of CHiPs and health facility staff;
- Qualitatively comparing how participant (PLWH and health staff) experience the models of care and experiences with the routine standard of care at the local health facilities;
- Qualitatively assessing participant (PLWH and health staff) perceptions about and experiences with the impact of the models of care on HIV services at the local health facilities.

5. To measure the health system costs of delivering the different community ART models.

In addition, we will measure the effect of the combined models on health facility crowding and waiting times as well as time to ART initiation of new patients in the 2 facilities (non- randomised comparison as both facilities have all models of care).

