4.0 Study Outcomes

The primary and secondary objectives for this study are listed in Section 2.2. The outcome measures for these objectives are listed below and will be measured in all study arms unless otherwise noted.

A. Primary Outcome – viral suppression at 12 months measured using the standard of care viral load testing equipment currently in place. Viral suppression will be defined according to National guidelines

B. Secondary Outcomes - these will include:

1. ***Viral suppression at 24 months*** – undetectable HIV viral load 24 months after entry into the models of care. This will be done as part of routine laboratory monitoring and measured using routine programmatic data.

2. ***Retention in care / Loss to Follow-up*** -Loss to follow-up from ART programmes describes all patients who are no longer in care and have an unknown outcome. A most useful definition of “loss to follow-up” should refer to patients with unknown outcomes(49). For this study, LTFU will be defined as “*no patient contact for 90 days or longer after the last given appointment*”.

Retention in care refers to *all patients retained in the HIV program*. Patients who are no longer retained in care with unknown outcomes will be classified as LTFU.

- In this study, retention will be defined as the number (%) of clients who are retained in the program at 6, 12 and 24 months after implementation of the intervention.
- The time to Lost to follow-up will be calculated in months according to the time interval between the dates of entry into the intervention to drop out, as recorded in the routine programmatic data.
- Proportion of patients that returned to mainstream care at 6, 12 and 24 months.

3. **HIV disease progression** – defined as having a new or recurrent WHO stage 3 or 4 condition after 6 months of ART, or a fall in CD4 count, (1). For patients with baseline CD4 count of < 200 cells/ μ l a fall of CD4 count to baseline or below after 6 months of ART; or persistent CD4 count < 100 cells/ μ l after 6 months of ART. (2). For patients with baseline CD4 count \geq 200 cells/ μ l, a persistent decline in CD4 count after two or more tests. For this study we will determine the following using routine health centre data:

- Proportion of patients who have had their CD4 count tests done at 6, 12 and 24 months after entering the models of care
- Proportion patients who developed a WHO stage 3 or 4 condition at 6, 12 and 24 months

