- Proportion of patients with CD4 count below 200 at 6, 12 and 24 months despite on treatment.

4. Death – defined as death at any point during the intervention due to any HIV related cause after enrolment into the study.

5. Participant choice of model and retention within that model. The following outcomes will be measured using programmatic and routine health centre data:

- Proportion of patients who enrolled into the models of care by sex
- Proportion (%) of eligible patients but refused to enter the model of care at baseline
- Proportion of patients who switched back to mainstream care at 6, 12 and 24 months and reasons for switching
- Number of club sessions and home visits that took place at 12 and 24 months after start of intervention

6. Drug Supplies –using routine health centre and programmatic data, we will determine:

- Number of groups/individuals missing at least one refill in the last 12 and 24 months (ART, Cotrimoxazole)
- Missed dispensations of ARVs at 6, 12 and 24 months.
- Proportion of pre-packed drugs returned to the clinic after a club session or home-based visit.
- Number of reported cases of ART drugs being pilfered after the start of the intervention.

7. Qualitative evaluation- of the acceptability and functioning of the two models of community ART delivery based on systematic structured observations of delivery, in-depth interviews and focus group discussions with key-informants (CHiPs, health facility staff) and longitudinal interviews with PLWH.

8. Economic Analysis – this will include:

- Measuring and comparing the incremental costs of the two intervention packages. The economic analysis will focus on measuring economic costs of the interventions from provider's perspective. The main focus will be on costs to the health services, including personnel, equipment and materials. The incremental cost of the interventions will be estimated by comparing costs of service provision and healthcare utilization with non-intervention healthcare facilities.
- Measure the impact of implementing the community ART delivery models on health systems and service delivery at local health centres in terms of technical and allocative efficiency of available HIV resource.

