5.0 Data Collection and Tools

Data will be collected at the following points:

Baseline

Three (3) months

Six (6) months

Twelve (12) months

Twenty four (24) months

Routine data will be collected using the national HMIS system and patient clinic records. At baseline, the following variables will be collected from patients to determine their influence on the outcomes:

- Age, sex, weight
- Recent CD4 count before enrolling into the models of care
- Viral load
- WHO stage at enrolment
- Date of starting ART
- Current drug regimen.

To maximize the validity of this information, the study team will work closely with the health centres to improve the collection and management of these routine data.

Data captured from the community models of ART delivery will be collected using the same hand held collection device being used in the main HPTN trial. A specific programme for this model will be installed in the device. This program is designed to maximize the quality of data collection using drop down lists and incorporating checks to avoid simple data entry errors. The CHiPs will undergo formal training on how to use the software to capture data at community level and sync it with the facility database and this training will be documented and retained in the site files.

Under the leadership of the Zambian Ministry of Health, the community ART steering committee has agreed upon a set of core indicators to be used to monitor and evaluate the community ART service delivery models being piloted by different partners. To facilitate the collection of the key indicators across both models, a list of common indicators will be used and this will be captured from both smart care and routine programmatic data.

Appendix 2 gives a detailed description of the data captured by the Chips in both Adherence clubs and home-based visits. The EDC program will capture data as required by the National ART community module for stable on care patients which has been developed by EGPAF and implementing partners. The following data will be captured in the device during the community ART model visits:

At clinic level:

- Patient ART registration details- Name, Sex, Age, ART number

At community Level (Adherence Clubs and Home based Visits)

- Date of visit
- Symptom Screen (fever, weight loss, cough, headache)
- Pregnancy screening for females
- Adherence counselling and types of counselling
- Pre-packed drugs dispensed
- Services referred for PMTCT, ART, STI, VMMC, etc.

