- Next community and clinic visit appointment

Data captured electronically during community visits will be linked to the HIV care databases at the health centre. The study team will work closely with the Ministry of Health and implementing partners

supporting the sites to collect relevant data from both the supply and demand side. Data that will be captured electronically during the club and home visits will be synced at the end of the day with the health care centre database. This is to ensure that indicators used for routine monitoring and follow-up will be entered in the current smart care system at facility level. The table below summarizes the core indicators that will be collected at both facility and community levels for the purpose of monitoring and evaluation.

Table 6: Common indicators for community ART models

Common Indicators for Community ART Models of Care		
Main	Core Indicator	Data Source
1. Recruitment	Proportion of patients enrolled into Home-Based ART models by sex	Smart care / HMIS
	Proportion eligible but refused	Consenting register
	Proportion of patients dropping out (within 1,3,6 and 12 months)	Routine data/ Programmatic data
	CD4 count at enrolment	Smart care
	Time on ART before enrolment	Smart care
2. Retention	Number (%) of clients retained at 1,3,6,12 and 24 months	Smart care
	Loss to follow up by reason:	Smart care
	
 • Dead • Transfer • Lost 	
	Number of patients returned to mainstream care (@ 3, 6, 12, 24 months)	Smart care
3. Laboratory	% of clients who developed an OI @ 3, 6, 12 and 24 months	Smart care and routine programmatic data
	Proportion of patients who have had viral loads within the last 6 months	Smart care and routine programmatic data
	Proportion of patients who have had CD4 count in the last 6 months	Smart care and routine programmatic data
	Proportion of patients with viral suppression at 12 and 24months	Smart care and routine programmatic data
4. Drug Supplies	Proportion of patients with CD4 count below 500 in the last 12 months despite treatment	Smart care and routine programmatic data
	Number of individuals missing at least one refill in the last 6 and 12 months	Smart care and routine programmatic data

Additional data collected for measuring the outcomes of the study objectives will be collected from patient clinical records. The key clinical indicators will be collected from smart care and HMIS and these includes:

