- Proportion of patients with continuous immunologic/virologic suppression
- Proportion of patients who develop opportunistic infections in the models of care
- Transition rates of newly eligible patients into the community models
- Transition rates of patients from community models back to facility care

Data Security

Data will be securely stored according to Ministry of Health and Smart Care guidelines that are already in place for all health care centres providing HIV care. All CHiPs involved in community of ART model delivery will have to sign a consent form as per smart care National Guidelines which explicitly explains data confidentiality and respect of clients. Data captured electronically in the device is encrypted and once it is synced with the health centre database, protected by Microsoft SQL security. Access of all data in the health centre database will be based on user right and every user in the facility has to agree to terms of use, which is currently in place. The Audit Trail in Smart Care that is currently in place in all ART health centres logs key events, which occur in the system. It logs information such as who logged into the system, which patient reports they run, changes to inventory and who created a back up. Every single interaction has the identifier of whoever entered the data as well. This trail will be used for security and audit purposes.

In order to obtain the data for monitoring and evaluation as well as for research purposes both by implementing partners and Zambart research teams, permission will be sought from the Ministry of Health. The study team will then periodically extract this data for measuring the outcomes of the study.

Investigators will also allow inspection of all study-related documentation by authorized representatives of the HPTN LOC, SDMC, LC, NIAID, US and in-country government and regulatory authorities and IRBs/ECs. A site visit log will also be maintained at the study site to document all visits.

Qualitative Data Collection

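### The measures listed for HIV disease progression do not measure progression as the same outcome defines it, so the two can classify one patient in opposite ways

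*Protocol*

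**What the plan says.** Secondary Objective 3 (Protocol 2.2.1) compares disease progression and death between community ART and clinic care, measured by "CD4 cell count, WHO staging events, death from routine health centre data".

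Section 4.0, outcome B.3, defines progression as a new or recurrent WHO stage 3/4 condition or a CD4 fall. The CD4 part has two rules:

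- Baseline below 200: "a fall of CD4 count to baseline or below after 6 months of ART", or a count that stays below 100.
- Baseline 200 or above: "a persistent decline in CD4 count after two or more tests. For this study we will determine the following using routine health centre data".

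The second quotation runs straight into the list of what will be determined: the share with a CD4 test done, the share with a WHO stage 3/4 condition, and "Proportion of patients with CD4 count below 200 at 6, 12 and 24 months despite on treatment".

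Section 5.0 has two further CD4 indicators. Table 6 includes "Proportion of patients with CD4 count below 500 in the last 12 months despite treatment", and a later list of clinical indicators includes "Proportion of patients with continuous immunologic/virologic suppression", which is not defined. For baseline data, section 5.0 says "At baseline, the following variables will be collected from patients to determine their influence on the outcomes", and the list includes "Recent CD4 count before enrolling into the models of care".

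**The concern.** The definition concerns change: a patient progresses by falling relative to an earlier count. The only CD4 result in the list is a level at one visit, which uses neither the baseline nor persistence. These are two different outcomes under one name, and a statistical analysis plan could not simply add detail. It would have to choose between them.

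At stake is what Secondary Objective 3 compares. Section 2.1 puts forward clinical and immunological outcomes alongside virological ones, and B.3 is where the immunological part is given a definition. If the choice between definition and list is left until data are available, it can be influenced by the results.

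There is also a smaller wording problem. The rule for baselines below 200 counts from 6 months of ART, as if baseline were the start of treatment. Section 3.1.3 admits only patients already on first-line treatment for more than 6 months, and the baseline CD4 to be collected is the recent count before enrolment.

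**Working it through.** The protocol gives no figure to reproduce here. The check sets definition against list, then sizes the mismatch under stated assumptions.

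**1. Matching the components**

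| Component of the definition | Measure in the list | Match |
|---|---|---|
| WHO stage 3/4 condition | WHO stage 3/4 condition | Yes |
| Baseline <200: fall to baseline or below | CD4 <200 | Always included, but unspecific |
| Baseline <200: persistent count <100 | CD4 <200 | Always included, but unspecific |
| Baseline ≥200: persistent decline | CD4 <200 | Only if the count crosses 200 |
| Any of the above, combined | None | No |

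The second and third rows follow by logic. A count at or below a baseline that is itself below 200 must be below 200, and so must any count below 100. A simulation rerun gave 100%, as it must. The first listed measure, CD4 test done, describes completeness of testing and not a patient outcome.

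**2. Worked patients (values assumed)**

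| CD4 at entry, then follow-up | Progression by definition? | Counted as CD4 <200? |
|---|---|---|
| 700, then 500, then 300 | Yes | No |
| 150, then 180 at each visit | No | Yes |
| 250, then 190, then 180 | Yes | Yes |

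The first two patients are classified in opposite ways. The third shows that the two outcomes overlap.

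**3. Illustrative size**

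The protocol gives no CD4 distribution, so all inputs are assumptions: median 300, 375 or 450; standard deviation of log CD4 0.4, 0.5 or 0.6; within-person coefficient of variation 15, 20, 25 or 30%. That makes 3 × 3 × 4 = 36 scenarios. True log CD4 is normal, each reading has independent lognormal error, and patients are grouped by measured enrolment CD4. Ranges are the minimum and maximum over scenarios.

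*CD4 <200 as a measure of progression*

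- No true change: 35-83% of patients below 200 at 12 months were already below 200 at entry. This is not the share misclassified, because some of them would meet the fall-to-baseline rule by chance.
- Patients at 200 or more at entry whose true CD4 halves and stays halved: 36-70% are below 200 at 12 months.
- The same group with a sustained 30% fall: 12-36% are below 200 at 12 months.

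*The rule for baseline 200 or above, with no true change and follow-up tests at 6 and 12 months*

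Three readings that differ only by independent error have 3! = 6 equally likely orders.

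- Read as two successive falls: 1 order of 6, or 1/6 = 17%.
- Read as both follow-up counts below baseline: baseline is the highest in 2 orders of 6, or 2/6 = 33%.

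Selecting patients whose measured baseline is 200 or more raises these slightly. The simulation gives 17-20% and 34-39% of that group, so 17-39% across the two readings.

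**The case against.** The strongest reply is that B.3 states a concept and then says how this study will measure it, much as B.2 does for loss to follow-up. On that reading the list governs, it fits the data named in Secondary Objective 3, and how the components combine belongs in the statistical analysis plan. That is a fair reading and it limits the point to wording. It does not remove the mismatch: B.3 gives rules specific to baseline CD4, and the list uses none of them.

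A reader might infer more than the documents support:

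- *That no listed measure captures a CD4 fall.* Too strong. CD4 below 200 includes every scheduled-test event under the rule for low baselines, and also patients who cross 200 from above. What is missed is persistent decline that stays at 200 or more.
- *That baseline is undefined.* Section 5.0 and Table 6 largely identify it as the enrolment count. Only the reference to 6 months of ART fits badly.
- *That the below-500 indicator contradicts the outcome.* Section 5.0 presents Table 6 as serving monitoring and evaluation.
- *That chance flags favour a non-inferiority conclusion.* The only margin, in section 7.0, is for death or non-suppression at 12 months. None is stated for progression.
- *That counting patients already below 200 biases the comparison.* Randomisation balances entry CD4 in expectation. The cost is sensitivity.

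It also stands that every CD4 input is assumed, and that sustained falls of 30% or 50% are hypothetical in a cohort selected as virologically suppressed.

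**Conclusion.** The point holds as an internal contradiction within one secondary outcome. B.3 defines progression partly by change from baseline, then lists a CD4 level that is unspecific for one of its CD4 rules and incomplete for the other, with no combined proportion to compare between arms. This rests on the text alone.

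The sizes are illustrative: 35-83% of patients below 200 at 12 months already below 200 at entry, and 17-39% of those at 200 or more flagged with no true change. They show that neither the list nor the definition as worded is a clean measure of progression. They are not forecasts for this cohort. The data are not the obstacle: enrolment CD4 is to be collected, so a fall can be derived wherever follow-up tests exist.

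Severity is minor. The primary endpoint, margin and power are not touched.

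**What to change.** Reconcile the definition and the list in B.3 so that one progression outcome is compared under Secondary Objective 3. There are two ways:

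1. Keep the definition, and list the proportion meeting it in full at 6, 12 and 24 months. State that baseline is the enrolment CD4, reword the reference to 6 months of ART to match, and have the investigators specify persistent decline so that it exceeds test-to-test variation.
2. Redefine the outcome as the listed measures, and drop the CD4-fall rules.

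Under either option, analyse CD4 below 200 adjusted for enrolment CD4, or as new cases among those at 200 or more at enrolment. Say whether the below-500 indicator and the undefined suppression indicator in section 5.0 are for monitoring only.

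The cost is wording in the protocol and the analysis plan, best settled before outcome data are seen. The downside falls on option 1. A rule that needs two follow-up counts cannot be applied to patients without them. CD4 comes from routine records and its completeness is itself a listed measure, so that loss could be large and should be reported by arm.

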3.1.3 Inclusion Criteria

All HIV adult patient (≥ 18 years) on first-line ART will be screened for eligibility at the health care facility serving the two communities. The eligibility criteria will include:

- All adult patients who are stable. To be considered “stable” a patient must:
 1. Be on first line treatment for more than 6 months and retained in care
 2. Must be virologically suppressed (according to the current standard of care definition of viral suppression)
 3. WHO stage I and II at the time of screening
- Patient resides within the clinic catchment area
- Willing to provide written informed consent and accept CHiPs intervention.

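### The CD4 part of the disease progression definition (Protocol 4.0, B.3) does not fit patients already stable on ART: with an enrolment baseline it counts chance variation as progression, and it does not match the measures listed under it

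*Protocol*

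**What the plan says.** Section 4.0, B.3 defines HIV disease progression as a new or recurrent WHO stage 3 or 4 condition, or a fall in CD4. The CD4 part depends on baseline CD4:

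- Baseline 200 or more: "a persistent decline in CD4 count after two or more tests". No size is given, and no reference point (below baseline, or below the previous test).
- Baseline under 200: "a fall of CD4 count to baseline or below after 6 months of ART", with no confirming test; or, as an alternative, a persistent count under 100, again once 6 months of ART have passed.

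Section 4.0 does not say which CD4 value is the baseline. The baseline list in section 5.0 contains one: "Recent CD4 count before enrolling into the models of care". Table 6 in the same section lists a CD4 count at enrolment. Neither lists a pre-ART count. Under section 3.1.3 a participant must "Be on first line treatment for more than 6 months and retained in care", be virologically suppressed, and be in WHO stage I or II at screening. No lower CD4 limit is set.

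B.3 then lists what the study will determine from routine data: "Proportion of patients who have had their CD4 count tests done at 6, 12 and 24 months after entering the models of care", the proportion developing a WHO stage 3 or 4 condition, and "Proportion of patients with CD4 count below 200 at 6, 12 and 24 months despite on treatment". The Table 6 indicator is CD4 below 500. Secondary objective 3 (section 2.2.1) compares progression between the community models and clinic care, using CD4 counts among other data.

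**The concern.** The wording suits people starting ART. Their CD4 should climb well above a pre-treatment value, so a return to that value after 6 months of treatment means something. Participants here passed the 6-month point before entry, so that window excludes nothing, and the CD4 value collected for them at baseline is normally an on-treatment one. Against such a baseline:

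- A sequence of 800, 790, 780 meets the clause for 200 or more.
- A change from 190 to 189 meets the clause for under 200, on one test.
- A persistent count under 100 may already be present on the day of enrolment, so a prevalent state would count as an outcome.

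At stake is the between-arm comparison of progression. Events produced by measurement variation at the same rate in every arm pull the arms together. In a trial whose hypothesis is that community delivery is not inferior, that could be read as reassurance.

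**Working it through.** The protocol states no progression rate, so there is no figure of its own to reproduce. The question is how often a patient with no true decline meets the rule if baseline is the enrolment CD4.

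**Inputs from the protocol.** The two CD4 clauses and follow-up tests at 6, 12 and 24 months (section 4.0); ART for more than 6 months and suppression at entry (3.1.3); recent CD4 before enrolment (5.0).

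**Inputs assumed (not in the protocol).** Within-person coefficient of variation (CV) 15-25%; true CD4 300-500 for the trend check; true trend 0 to +100 cells per year.

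**1. Baseline 200 or more, two tests, no true trend.** With independent errors and no ties, the three counts are exchangeable, so all 3! = 6 orderings are equally likely and the CV does not matter.
- Both later counts below baseline (baseline is the largest of three): 1/3 = 33.3%.
- Each count below the one before: 1/6 = 16.7%.

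Restricting a simulated population to measured baselines of 200 or more changes this little: about 35% and 17-18%.

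**2. Baseline 200 or more, three tests, no true trend.** There are 4! = 24 equally likely orderings.

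| Reading of a persistent decline | Chance rate |
|---|---|
| Falling at every test | 1/24 = 4.2% |
| All three below baseline | 1/4 = 25.0% |
| Any two successive falls | 1/6 + 1/6 - 1/24 = 7/24 = 29.2% |
| Any two consecutive tests below baseline | 1/4 + (1/4)(2/3) = 5/12 = 41.7% |

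**3. Baseline 200 or more, rising CD4, tests at 6 and 12 months.** Lognormal simulation, 200,000 patients per setting; ranges run over the assumed CVs and CD4 levels.

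| True rise per year | Both below baseline | Successive falls |
|---|---|---|
| +25 cells | 23-29% | 10-14% |
| +50 cells | 14-26% | 6-12% |
| +100 cells | 5-19% | 2-8% |

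**4. Baseline under 200.** One value at or below baseline suffices. Pure exchangeability gives n/(n+1) for n tests: 1/2, 2/3, 3/4. This is too high, because patients whose measured baseline is under 200 tend to measure higher next time. Two simulations allowing for that, with no true trend (assumed median 400, log SD 0.45; and median 450, log SD 0.5), give 26-34% at one test and 49-59% at any of three.

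**5. Role of the missing size.** Suppose, for illustration only, that both the 6- and 12-month counts had to be at least 30% below baseline. With no trend the 33% becomes 1.1%, 3.3% or 6.0% at a CV of 15%, 20% or 25%. At 50% below it is under 0.5%.

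**6. Effect on a comparison.** Let a share q of non-progressors be misclassified equally in both arms. The observed rate is p + (1 - p)q, and the observed difference is the true difference times (1 - q). A true difference of 5 points, taken for illustration, becomes 5 x 5/6 = 4.2 points at q = 1/6 and 5 x 2/3 = 3.3 points at q = 1/3.

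**7. Definition against listed measures.** The definition uses falls from baseline and a level of 100. The list beneath it uses a level of 200. Table 6 uses 500. No listed measure is the proportion meeting the fall rule.

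**The case against.** The strongest objection is that the fall rule may never be analysed. Directly after the definition the protocol says what will be determined, and that list contains tests done, WHO stage 3 or 4 conditions and CD4 below 200. This stands as a limit on the practical effect. It does not rescue the text: the outcome is defined by one rule and reported by another, and an analyst who follows the definition gets the chance rates above.

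Second, the on-treatment baseline is inferred. Section 4.0 does not state it, and the list in section 5.0 is introduced as variables whose influence on outcomes will be examined. With a pre-ART baseline taken from clinic records, the chance rates above would not apply. This also stands, so the result is conditional. But no pre-ART CD4 is listed, and entry requires more than 6 months of ART.

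Third, the size of a decline is something a statistical analysis plan often sets. That is fair for the clause for 200 or more. It does not cover the clause for under 200, which fixes a rule (at or below baseline, one value), or the ART-duration window, which cannot separate new events from existing ones here.

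A reader might infer more than the protocol supports:

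- *That one in six to one in three of all participants would be misclassified.* Those figures need a baseline of 200 or more, exactly two tests, no true trend, and one of two readings of the clause.
- *That the non-inferiority conclusion is biased.* The 5% margin in section 7.0 belongs to the primary endpoint; progression has none. Noise also widens intervals as well as shrinking differences: raising a 5% rate to 0.05 + 0.95/3 = 36.7% multiplies the standard error by about sqrt(0.367 x 0.633 / (0.05 x 0.95)) = 2.2.
- *That unequal CD4 testing between arms will create false differences.* More tests do give more chance events under some readings, but no difference in testing is documented, and the proportion tested is already a listed measure.
- *That the economic results are affected.* Section 5.0 says progression data will be used there, but not that the fall rule will be.

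**Conclusion.** The point holds in conditional form. The CD4 clauses do not suit a population already suppressed on ART, and the definition and the measures listed under it disagree. If the definition is applied to the enrolment CD4, a substantial share of patients without true decline would be called progressors. The exact size depends on the reading, the number of tests and the CD4 trend, and no single rate can be fixed from the protocol. The exchangeability figures need only a flat true CD4 and independent errors; the rising-CD4 and under-200 figures rest on the assumed variability and CD4 distributions. The problem of a count under 100 already present at entry needs no assumption beyond the absence of a lower CD4 limit in section 3.1.3, though how many such patients would enrol is unknown. The consequence is confined to secondary objective 3. It should be corrected, but it does not threaten the main result.

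**What to change.** Reword B.3 as follows:

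- State that baseline is the enrolment CD4 (the recent count before enrolment).
- Count only WHO stage 3 or 4 conditions and CD4 events with onset after enrolment, in place of the window based on 6 months of ART.
- Delete "a fall of CD4 count to baseline or below after 6 months of ART" and the unsized "a persistent decline in CD4 count after two or more tests".
- Define the CD4 component by one rule aligned with the listed measures. Examples are a confirmed CD4 below 200 in participants at or above 200 at enrolment, or a confirmed fall of a prespecified size larger than within-person variability. The sponsor should choose and justify the size; the 30% and 50% figures above only illustrate why a size is needed.
- Say how the Table 6 indicator (below 500) relates to this outcome, for instance as programme monitoring only.
- Report the result with the proportion tested in each arm, which B.3 already plans to collect.

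This is a change of wording, with no new data and no added test schedule. The cost is fewer events: small declines no longer qualify, and a confirmed rule cannot be met by a participant with only one follow-up count. The level-based example also gives no CD4 event to someone who enters below 200, so the sponsor should say how that group is handled.
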